REPORTING AND RESPONSE DEFINITION: These are not strictly quantitative assays. IgG response will be reported graphically demonstrating sera dilution curves, and by titer – defined as the highest sera dilution at which IgG responses are detectable above the mean + 3 standard deviations of the negative control. A positive IgG response resulting from immunization will be defined as an antigen-specific IgG titer at least 4-fold higher than the baseline titer detectable at the 6-month post-treatment time point (or other post-treatment time point evaluated).

v. Assessment of antigen-spread to other prostate-associated antigens

High-throughput immunoblot (HTI): An exploratory objective of the study will be to determine if patients treated develop "off-target" prostate cancer antigen-specific immune responses as evidence of antigen spread. Future studies may evaluate T-cell responses to non-targeted antigens. However, the primary evaluation will be to evaluate IgG responses to a panel of prostate-associated antigens as we have previously reported in patients treated with vaccines or other immune-modulating agents [88, 89, 90]. IgG specific for 126 antigens, including 29 cancer-testis antigens [91, 92] and 97 prostate antigens frequently immunologically recognized [93, 94, 95, 96] will be identified by screening a high-density phage array expressing these individual antigens, as we have previously reported [88, 90, 91]. An alternative to this approach may include the evaluation of responses to panels of protein antigens fixed to support membranes provided by commercial vendors. The primary analysis will be conducted using sera obtained at 6 months, and compared with IgG responses identified at baseline, to determine whether IgG specific for individual antigens are elicited over time. Other time points will be assessed to determine the durability and kinetics of immune response development, and confirmatory ELISA studies will be performed where feasible.

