REPORTING AND RESPONSE DEFINITION: A positive IgG response will be defined as an immunoreactive spot to a defined antigen, scored by at least 3 of 4 independent reviewers, and detectable to at least 2 of 3 replicates per immunoblot membrane as previously described [88, 97], or by statistically defined criteria using commercial antigen sources. An IgG response resulting from immunization will be defined as an immunoreactive antigen identified at the 6-month (or other post-treatment time for subsequent analyses) time point that was not identified at the pre-treatment time point.

o. Histopathology Evaluation

Tissue biopsies will be obtained from metastatic bone lesions from a small subset of subjects (the same lesion per patient) prior to treatment and at week 12. Bone biopsies are required due to their correlation with the NaF PET/CT imaging. If the pre-treatment site is not appropriate for the week 12 biopsy, a new site (bone) may be selected. Archived tissue corresponding to the selected site may be obtained (if available) in order to provide a matched set for comparison. The purpose of these studies is to determine whether immunization affects PD-L1 expression in the tumor (likely by eliciting tumor antigen-specific T cells secreting IFNy), whether concurrent treatment with anti-PD-1 mAb leads to an increase in infiltration of CD8+ T cells, and whether treatment increases expression of other T-cell regulatory ligands on T cells (PD-1, CTLA-4, TIM-3, BTLA, LAG-3) or tumors (e.g. HVEM, phosphatidyl serine, PD-L2). Consequently, biopsy specimens obtained pre-treatment and after 12 weeks will be stained with antibodies specific for CD3, CD4, CD8, FoxP3, PD-1, CTLA-4, TIM3, BTLA, LAG-3, PD-L1, PD-L2, phosphatidyl serine, HVEM and potentially other markers. Other stains may be performed as well. Staining and quantification will be reviewed and may include evaluations including: number of CD8+ T cells per field, CD4+FoxP3+ (Treg):CD8+ T cell ratio, PD-L1 expression, and whether these or the expression of CD8+ T cells expressing one regulatory receptors (or tumor cells expressing one or more regulatory ligands) change from pre-treatment to the 12 week time point.

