Generalized linear models with a logit link function will be used to evaluate PAP-specific and ARspecific antibody responses following treatment with pembrolizumab and DNA vaccine(s), and to determine whether treatment with either sequence elicits immunologic antigen spread to other prostate associated antigens. Logistic regression analysis will be utilized to determine whether pre-existing antigen-specific immunity is predictive of immunological or objective clinical response. The interaction term between pre-existing antigen-specific immunity status and treatment arm will be included in this model and evaluated. Analogously, a generalized linear model with subject specific random effects will be used to determine whether early changes in bone observed by NaF PET/CT are associated with immunological or objective clinical response, or pathological changes associated with immune-cell infiltration. The number and frequencies of second PSA responses in patients treated in follow-on courses will be summarized in tabular format. The stratified (by randomization strata) Mantel-Haenszel test will be used to compare second PSA response rates between study arms. Bacterial, viral and archeal species loads identified from the bioinformatics analysis of the microbiome samples will be compared between pre- vs. post-treatment assessment using a paired t-test. The false discovery rate will be controlled using the Benjamini-Hochberg False Discovery Rate (FDR) method. Logistic analyses will be conducted to determine whether changes in gut microbiota are associated with clinical response.

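### The antigen-spread definition counts new positives among 126 antigens, ignores lost positives and sets no chance rate, so it leans towards finding spread within each arm

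*Combined protocol and SAP*

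**What the plan says.** Section 10, under Immunological Monitoring, item v, plans a high-throughput immunoblot for "IgG specific for 126 antigens, including 29 cancer-testis antigens" and "97 prostate antigens frequently immunologically recognized". The primary comparison is month-6 sera against baseline sera.

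A spot is positive if it is "scored by at least 3 of 4 independent reviewers" and "detectable to at least 2 of 3 replicates per immunoblot membrane". If commercial antigen sources are used instead, unspecified statistical criteria apply. The step from a positive spot to a treatment effect is this: "An IgG response resulting from immunization will be defined as an immunoreactive antigen identified at the 6-month" time point (or a later one in subsequent analyses) "that was not identified at the pre-treatment time point".

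For checking, item v adds that "confirmatory ELISA studies will be performed where feasible" and that other time points will be used to look at durability and kinetics. Neither check is part of the definition.

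Section 11, Exploratory Analyses, names generalized linear models with a logit link, among other things "to determine whether treatment with either sequence elicits immunologic antigen spread to other prostate associated antigens". It does not list the model terms. False discovery rate control is mentioned after the microbiome comparison and not for this panel. Section 11, General, says that there is otherwise no multiplicity adjustment and that a detailed SAP will be written before the final analysis.

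**The concern.** The definition attributes every negative-to-positive change to immunization. An antigen read twice can change call without any biological change, and such changes go in both directions. A rule that keeps the gains and discards the losses can only move the answer one way.

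The other assays in Section 10 guard against this. ELISPOT, proliferation and intracellular cytokine staining each ask for a 3-fold rise over baseline and a minimum frequency, and ELISA asks for a 4-fold titer rise. Only the 126-antigen screen accepts a bare change of call.

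At stake is exploratory objective 2, whether treatment with either sequence elicits spread. That is a within-arm question. Both arms receive vaccine and pembrolizumab, so no untreated group supplies a background rate, and the plan states none.

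**Working it through.** **Inputs from the documents.** Panel: 29 + 97 = 126 antigens, which agrees with the stated total. Direction counted: gains only. Size: at most 30 patients per arm, and fewer in practice because immune blood is drawn only at the lead site.

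**Inputs not in the documents (assumed).** q is the chance that one antigen with no true change is called negative at baseline and positive at month 6, after the reviewer and replicate rules; range 0.01% to 2%. Antigens are taken as independent. A patient is called a spread case with at least one new antigen; the plan sets no such cut-off.

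**Step 1. Why losses measure the noise.** If an antigen has the same call probability p at both visits, P(gain) = (1 − p)p and P(loss) = p(1 − p). They are equal for every p, so with no true change expected gains equal expected losses. The definition uses only the first.

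**Step 2. Share of patients labelled by chance.** Expected gains per patient = 126q; P(at least one) = 1 − (1 − q)^126.

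| q per antigen | Expected gains | At least 1 gain |
|---|---|---|
| 0.01% | 0.013 | 1.3% |
| 0.1% | 0.126 | 11.8% |
| 0.25% | 0.315 | 27.0% |
| 0.5% | 0.63 | 46.8% |
| 1% | 1.26 | 71.8% |
| 2% | 2.52 | 92.2% |

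A quarter of patients is reached at q of about 0.23% and half at about 0.55%. The cut-off matters: at q = 0.5%, at least two new antigens gives 13.2% and at least three gives 2.6%.

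**Step 3. What the replicate rule achieves.** Let f be the false-positive rate of a single replicate, with replicates independent. The call rate is c = 3f² − 2f³ and q = c(1 − c). Then f = 1% labels 3.7% of patients, 2% labels 13.9%, 3% labels 28.3% and 5% labels 59.8%. So the rule helps a good deal when single-replicate error is low and random.

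It does not help near the detection limit. With f = 0.5, c = 3(0.25) − 2(0.125) = 0.5, so the antigen is still called positive half the time and its gain probability is 0.5 × 0.5 = 0.25. Two such antigens give a gain in 1 − 0.75² = 43.8% of patients, and three in 1 − 0.75³ = 57.8%. Stable true positives can also flip. As an illustration, ten antigens each called positive 90% of the time give 10 × 0.9 × 0.1 = 0.9 expected gains, and 1 − 0.91^10 = 61% of patients with at least one.

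**Step 4. Between arms.** If chance labels a share π in both arms, and true spread t adds to it independently, the observed share is π + (1 − π)t. The arm difference is then (1 − π)(t2 − t1). At q = 0.5% the factor is 1 − 0.468 = 0.532. The difference shrinks but stays zero when t1 = t2.

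**Step 5. With losses counted.** At q = 0.5% and 30 patients, chance gives about 30 × 0.63 = 18.9 gains and 18.9 losses. In simulation with equal rates, an arm-level paired t-test of gains minus losses rejected 4.8% to 5.3% of the time at a nominal one-sided 5% (10 to 30 patients, q from 0.25% to 1%). The signed-rank version proposed below was not simulated. Netting does not rescue a per-patient label: at q = 0.5%, 29.6% of no-effect patients still have a net gain above zero.

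**The case against.** The best defence is that the plan has real safeguards. A spot must pass both the reviewer and the replicate rule, ELISA follow-up is planned, and later time points would tend to expose isolated false positives. With single-replicate error of 1% and independence, only 3.7% of patients would be labelled by chance. This stands as a limit on size. It does not remove the bias: the rules act on each call and not on the asymmetry between gains and losses, they do not help borderline antigens, and neither ELISA nor persistence is required for a response.

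A reader might infer that ordinary assay noise will show spread in most patients. The documents do not support that. They give no error rate, the assay's performance is left to cited reports, and the response is defined per antigen, with no rule that one new antigen makes a patient a case.

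A reader might also infer that the logit model can only compare the two vaccinated arms. Section 11 lists no terms, and a model of positivity with a before/after term would use losses as well as gains. The fair statement is that the model is unspecified, while the response definition that it would naturally use is gain-only.

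Finally, losses need not be pure noise. True waning would be subtracted too, and no within-arm count separates treatment from disease course. That limits what the remedy can show, but does not justify discarding the losses.

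**Conclusion.** The concern holds in a limited form. The written rule is one-directional over 126 antigens, sets no minimum change and no chance rate, and attributes each gain to immunization, so the within-arm answer to exploratory objective 2 is biased towards spread.

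The direction follows from the definition whenever calls are imperfectly repeatable. The size cannot be fixed from the documents. Under independence and a one-antigen cut-off, the share of patients labelled by chance runs from about 1% (q = 0.01%) to over 90% (q = 2%), and 47% at 0.5% is one point on that range and not an estimate. Correlated errors, such as a membrane or batch effect, would change these shares.

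It would be too strong to conclude that the Arm 1 versus Arm 2 comparison is biased: with equal noise it is only diluted. The objective is exploratory and no decision is tied to it, so this is a worthwhile improvement and not a threat to the trial.

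**What to change.** In the SAP, for each patient with paired sera, count gains and losses over the same 126 antigens (or over whichever panel is finally used). Test gains minus losses within each arm and pooled with a Wilcoxon signed-rank test, stating how zeros and ties are handled, since many patients may have a net count of zero. Compare the net count between arms. Report gains alone, and any per-patient spread label with its cut-off, descriptively only.

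The cost is SAP wording; the membranes and readings are unchanged. There are three downsides. Fewer patients will be described as having spread. True waning of responses is subtracted along with noise. The test removes symmetric assay noise but not real time trends unrelated to treatment, so a positive result still should not be read as proof of a vaccine effect.

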11. STATISTICAL CONSIDERATIONS

r. Overview

This is a 1:1 randomized, open-label, multi-institution phase II trial designed to evaluate the immunological and clinical effect of one versus two DNA vaccines, used as T-cell activating therapies, and given concurrently with pembrolizumab. The rationale for conducting this trial is summarized in Section 2.

s. Objectives

Primary Objective:

To determine the 6-month progression-free survival rate in patients with metastatic, castration-resistant prostate cancer (mCRPC) treated with pembrolizumab in combination with one versus two DNA vaccines as T-cell activating agents

Secondary Objectives:

- 1. To determine the overall objective response rate (using Prostate Cancer Working Group 3 (PCWG3) criteria)
- 2. To determine the PSA response rate (decline > 50%)
- 3. To determine the median progression-free survival rate
- 4. To determine median duration of PSA and/or objective response in responding individuals
- 5. To determine the overall survival
- 6. To determine whether the development of antigen-specific Th1 immunity elicited with treatment to either antigen (PAP or AR) is associated with PSA response
- 7. To evaluate the safety and tolerability of pTVG-HP DNA vaccine with or without pTVG-AR DNA vaccine and pembrolizumab

Exploratory Objectives:

- 1. To evaluate PAP-specific and AR-specific antibody responses following treatment with pembrolizumab and DNA vaccine(s)
- 2. To determine whether treatment with either sequence elicits immunologic antigen spread to other prostate associated antigens
- 3. To determine whether pre-existing antigen-specific immunity is predictive of immunological or objective clinical response
- 4. To determine, in a subset of patients, whether early changes in bone observed by NaF PET/CT are associated with immunological or objective clinical response, or pathological changes associated with immune-cell infiltration
- 5. To determine second PSA response rates in patients treated in follow-on courses
- 6. To determine whether treatment elicits changes in the gut microbiota composition
- 7. To determine whether changes in gut microbiota are associated with clinical response (PSA decline > 50%)

t. Study Design

The study is designed as a randomized, two-arm, open-label, multi-institution phase 2 trial. Study arms will be defined as follows:

Course 1:

Arm 1: 100 μg pTVG-HP administered intradermally (i.d.) days 1, 8 + 200 mg

pembrolizumab IV day 1 of 21-day cycles x 8 cycles

Arm 2: 100 μg pTVG-AR i.d days 1, 8 + 200 mg pembrolizumab IV day 1 of 21-day cycles,

for cycles 1, 2, 5 and 6 alternating with

100 µg pTVG-HP i.d. days 1, 8 + 200 mg pembrolizumab IV day 1 of 21-day

cycles, for cycles 3, 4, 7 and 8

Patients who have not come off trial at the end of cycle 8 (month 6) will continue to receive pembrolizumab at 3-week intervals, up to a total of 2 years (32 cycles) of treatment, or until evidence of radiographic progression. If prior to 2 years, and in the absence of radiographic progression, patients with rise in PSA (25% over month 6 value and with minimum rise of 2 ng/mL) will resume vaccination in follow-on courses:

Arm 1: 100 μg pTVG-HP i.d. days 1, 8 + 200 mg pembrolizumab IV day 1 of 21-day cycles

x 4 cycles

Arm 2: 100 μg pTVG-AR i.d days 1, 8 + 200 mg pembrolizumab IV day 1 of q 21-day

cycles, for two cycles followed by

100 µg pTVG-HP i.d. days 1, 8 + 200 mg pembrolizumab IV day 1 in 21-day

cycles, for two cycles

Eligible subjects will be randomly assigned in 1:1 fashion to either Arm 1 or Arm 2.

u. Randomization and Stratification

Eligible patients will be randomized to the two study arms with an allocation ratio of 1:1. The randomization will be stratified by institution and prior treatment (or not) with prior second generation AR targeting agents. Treatment arm assignment will be made by biostatics/investigational pharmacy after a patient has been registered.

v. Sample Size and Power Calculation

The expected 6-months PFS rate in Arm 1 (pTVG-HP DNA vaccine and Pembrolizumab) in this patient population is 20-30%. It is hypothesized that adding pTVG-AR DNA vaccine (Arm 2) will increase the 6-months PFS rate to at least 55%. The following table shows the required sample sizes for detecting various differences in the 6-months PFS rates between the two study arms, assuming 80% power and a one-sided 0.10 significance level. As this is a phase II study, a less stringent significance level of 0.10 rather than the traditional 0.05 level will be used for the primary efficacy evaluation.

Required sample sizes to detect a difference of 20-30% vs. 50-60% in the 6-months PFS rates between arms			
	6-mont	hs PFS rate in	ı Arm 2
6-months PFS rate in Arm 1	0.50	0.55	0.60
0.20	54	42	32
0.25	80	58	44
0.30	124	82	58

A sample size of 60 evaluable patients (30 per arm) is proposed for this study. The following table shows the attainable power levels for detecting various differences in the 6-months PFS rates between arms with a sample size of 30 patients per arm at the one-sided 0.10 significance level.

Attainable power levels for detecting various differences in the 6-months PFS rates					
between arms with the proposed sample siz	e of 30 patients	per arm			
6-months PFS rate in Arm 2					
6-months PFS rate in Arm 1	0.50 0.55 0.60				
0.20	88.8%	94.8%	98.0%		
0.25	77.1%	87.4%	94.1%		
0.30	62.0%	75.8%	86.6%		

Hence, the proposed sample size of 60 evaluable patients will provide 77-98% power to detect an anticipated difference in the 6-months PFS rates of 20-25% in Arm 1 vs. 50-60% in Arm 2. Analogously, the sample size will provide between 62-94% power to detect a difference of 25-30% in Arm 1 vs. 50-60% in Arm 2. PASS software (NCSS, LLC) version 12 was used to conduct the samples size calculations.

w. Analysis

i. General

This section outlines the statistical analysis strategy and procedures for the study. Prior to the analysis of the final study data, a detailed Statistical Analysis Plan (SAP) will be written describing all analyses that will be performed.

Summary tabulations will be presented that will display the number of observations, mean, standard deviation, median, range, minimum, and maximum for continuous variables and the number and percent per category for ordinal and categorical data. All endpoints of this study will be presented graphically where possible using boxplots and histograms for continuous variables and (stacked) bar charts for categorical variables. Data analysis will be performed using SAS® (SAS Institute Inc., Cary, North Carolina) version 9.4 or greater.

There are many comparisons made between the two trial arms for multiple measurements, both clinical and laboratory. However, since this is an early phase efficacy trail, no adjustment will be made for multiple comparisons.

ii. Analysis Populations

The ITT population consists of all patients who are randomized. The per-protocol population consists of all evaluable patients, i.e., patients who have been treated according to protocol (all inclusion/exclusion criteria are satisfied, and adequate treatment compliance (complete treatment with pTVG-HP DNA vaccine alone or in combination with pTVG-AR DNA vaccine and Pembrolizumab to at least week 12). The safety population consists of all subjects who received at least one dose of pTVG-HP DNA vaccine with or without pTVG-AR DNA vaccine and Pembrolizumab. All primary, secondary and correlative outcomes will be analyzed for both the IIT and per-protocol population. The IIT population will be the primary analysis population. Safety will be evaluated using the safety population.

To attain 60 evaluable participants, the trial may randomize more than 60 participants if any are deemed unevaluable.

iii. Baseline Comparability

All measurements (variables) collected at baseline will be summarized and compared between study arms. These include demographic variables, ECOG PS, lab parameters (CBC, chemistry panel, serum testosterone, PSA and PAP) medical history information and CTCs. Comparisons between study arms of baseline variables on a continuous scale will be performed using a two-sample t-test and/or nonparametric Wilcoxon Rank Sum test. Comparisons between study arms of baseline variables on a categorical scale will be performed using a chi-square or Fisher's exact test.

iv. Analysis of Primary Endpoint

The 6-month PFS rate will be calculated for each study arm along with the corresponding two-sided 95% confidence interval which will be constructed using the Wilson score method. Patients who withdraw from the study without a progression or death event before the 6-month assessment will be excluded from this analysis. The stratified (by randomization strata) Mantel-Haenszel test will be used to compare the 6-months PFS rates between study arms.

v. Analysis of Secondary Endpoints

F.5.1. Overall Objective Response Rate and PSA Response Rates

The number of responses will be summarized in tabular format, stratified by study arm. Of note, objective response rate using radiographic criteria will apply only to subjects with RECIST-measurable disease (i.e. not subjects with bone-only metastatic disease). Response rates (overall objective response and PSA response) will be calculated for each study arm along with the corresponding two-sided 95% confidence interval which will be constructed using the Wilson score method. The stratified (by randomization strata) Mantel-Haenszel test will be used to compare the overall objective response rates between study arms.

F.5.2. Progression-Free Survival and Overall Survival

Progression-Free and overall survival will be analyzed using the Kaplan-Meier method. Median PFS and OS will be calculated for each study arm and reported along with the corresponding 95% confidence intervals will which will constructed using the nonparametric Brookmeyer and Crowley method. The stratified (by randomization strata) log-rank test will be used to compare PFS and OS between study arms.

F.5.3. Antigen-specific Th1 immune Response

The number and frequencies of antigen-specific Th1 immune responses will be summarized in tabular format for each study arm and both study arms combined. A generalized linear model with a logit link function will be used to evaluate whether antigen-specific Th1 immunity elicited with treatment to either antigen (PAP or AR) is associated with PSA response. The interaction term between treatment arm and antigen-specific Th1 immune will be included in this model.

F.5.4. Analysis of Toxicity Rates and Serum Chemistry Parameters

Subjects will be evaluated at each visit by a review of systems based on the most recent version of the NCI common toxicity criteria. Furthermore, serum chemistries, including renal function tests, blood counts, liver function tests, and serum amylase, will be evaluated at 6-12 week intervals. Toxicities will be summarized by type and severity in tabular format. Toxicity rates (grade 2, grade 3, grade 4, grade \geq 2, grade \geq 3, etc.) will be calculated for each study arm and reported along the corresponding 95% confidence intervals. The 95% confidence intervals will be constructed using the Wilson score method. Fisher's exact test will be used to compare toxicity rates between study arms. Serum chemistry and amylase parameters will be summarized using standard descriptive statistics. Changes from the baseline assessment will be evaluated using a paired t-test.

vi. Exploratory Analyses

Generalized linear models with a logit link function will be used to evaluate PAP-specific and ARspecific antibody responses following treatment with pembrolizumab and DNA vaccine(s), and to determine whether treatment with either sequence elicits immunologic antigen spread to other prostate associated antigens. Logistic regression analysis will be utilized to determine whether pre-existing antigen-specific immunity is predictive of immunological or objective clinical response. The interaction term between pre-existing antigen-specific immunity status and treatment arm will be included in this model and evaluated. Analogously, a generalized linear model with subject specific random effects will be used to determine whether early changes in bone observed by NaF PET/CT are associated with immunological or objective clinical response, or pathological changes associated with immune-cell infiltration. The number and frequencies of second PSA responses in patients treated in follow-on courses will be summarized in tabular format. The stratified (by randomization strata) Mantel-Haenszel test will be used to compare second PSA response rates between study arms. Bacterial, viral and archeal species loads identified from the bioinformatics analysis of the microbiome samples will be compared between pre- vs. post-treatment assessment using a paired t-test. The false discovery rate will be controlled using the Benjamini-Hochberg False Discovery Rate (FDR) method. Logistic analyses will be conducted to determine whether changes in gut microbiota are associated with clinical response.

